**Practices Statement**

This study is to be performed in full compliance with the protocol and applicable oversight body and regulatory requirements. All required study documentation and data will be archived in accordance with preauthorized policies and procedures.

## **1. Background**

Opioid use disorder affects an estimated 1.9 million people in the United States (2014) with an estimated 586,000 of cases related to heroin use, and with all patients suffering harms as a result of this chronic condition. The economic impact of illicit prescription opioid abuse alone is estimated to be \$53-72 billion, imposing high costs to society as a whole. In previous work, NXTech developed an mHealth application derived from cognitive science findings. In this study mHealth-based exercises are provided to healthy individuals to inform design of optimal interventions for OUD.

## **2. Protocol and Procedures**

This study consists of a feasibility study of the mHealth platform for cognitive training completion in two configurations.

Participants in the beta test (see SAP for subjects recruitment targets) will be invited to participate by investigators, in a remote study coordinated by the investigator institution.

IRB approval will be obtained by the local host institution prior to any human subjects activities. If no waiver of written consent is granted under IRB oversight, subjects will provide informed consent in writing before enrollment. There is no more than minimal risk expected to participants in the study.

The experiments will be completed online and users will be required supply their own standard electronic mobile device to complete the study.

Participants will be recruited to engage with the application for a recommended period of 150 minutes per week for 8 weeks total, with enrollment as detailed in Section 3. During the study period, we will evaluate application feasibility by gathering optional open-ended and closed-ended feedback along with required measures of user adherence to the intervention and requested measures of task performance as delivered on a numerical score basis by the mHealth application.

## **3. Recruitment and Enrollment**

Recruitment will proceed through two stages. First, participants will be pre-screened for their eligibility for the second stage and their baseline rates will be determined, in addition to an optional survey relating to health behaviors, as the selection of the site investigator and subject to remote platform screening acceptance. Second, participants meeting eligibility criteria below and who occupy the upper 25% quartile of scored choices will be invited to an 8-week long follow-up study.

Compensation for participation will be set at a rate of \$5 per hr (or as adjusted based on prevalent remuneration rates at the time of study execution).

Subjects will only be tracked by an assigned numeric ID that is unassociated with an individual's personally-identifiable information.

Inclusion Criteria are as follows:

Age 18 years and above

Fluent in English  
Resides in the United States  
Score on prescreen task is in 25% quartile  
Familiar with smartphone device app installation and device usage  
Possesses a compatible smartphone

Exclusion Criteria: None if qualified under Inclusion Criteria

#### **4. Compliance Procedures**

This study will be performed in accordance with Protocol requirements and applicable oversight body policies.

Data collection will be primarily in electronic format. All required study documentation and data records will be archived in accordance with preauthorized policies and procedures. Investigators will assure that either a waiver of consent is granted under IRB approval, or that informed consent is obtained prior to performing any research procedures. Investigators will ensure that all participants meet eligibility requirements, and that the study is conducted according to the IRB-approve research plan and in accordance with the Federalwide Assurance certification of the site.

Adverse events and serious adverse events are not expected but will be recorded and addressed under institutional procedures.

Documentation and data will be stored and archived in a secure format for at least 2 years and for the duration required by the Sponsor and collaborating sites.

#### **5. Biological Samples**

None will be collected or analyzed.

Protocol NX-21270

Cover Sheet

Official Title: Boost Study 21270 (Cognition)

ClinicalTrials.gov ID (NCT number): NCT05990335

Document Date: April 17, 2022

Document Description: Statistical Analysis Plan

Confidentiality Statement

This document contains confidential and proprietary information of sponsor NXTech Inc, provided solely for the purpose of reviewing or performing this study under compliance of federal reporting requirements; and is not intended as public disclosure or other dissemination activity which may in any way limit intellectual property rights assertions by the sponsor.

1. Study Design and Power

The study design reflects an interventional, between-subjects and within subjects mixed design, with major variables of high/low group intervention/control after exposure to cognition exercises under the custom mHealth application configurations denoted as “Group I” and “Group C” respectively.

The enrollment target is 120 participants as described in the Protocol, for a total of 30 participants per group. Sample size is based on a power analysis conducted on Steele et al, 2019; which indicated the need for a final sample of at least 25 participants per group to achieve an observed power > 0.8 to detect a moderate effect size of 0.3-0.4 at an alpha level of 0.05.

During pre-screening, participants who are invited but choose not to accept enrollment in the study may be replaced by screening additional participants and selecting individuals that fall within the originally defined ranges. Any participants who disenroll in the first 2 weeks may be replaced with new subjects (rolling basis) to minimize overall participant loss. With an enrollment of 30 participants per group, this will allow an additional loss of 5 participants per group while still achieving the final target sample size.

2. Analysis Methodology

Upon completion of the study, a comprehensive analysis will include pre-specified analyses:

- A. Task Completion (primary) endpoint will be evaluated per Group, as whole-number percentage of subjects completing minimum usage, per week. Mean and standard deviation will be reported for each Group.
- B. Task Performance (secondary) endpoint will be calculated from cognition index scores as mean and standard error, per Group, as a differences-based analysis for the subgroup of subjects completing all study weeks per arm; using, as appropriate, a multi-level model to account for individual differences per Kirkpatrick et al, 2018, provided that random effects within models are not overparameterized (Bates et al, 2016). As appropriate, we will perform analysis checks for overparameterization to minimize loss of statistical power in an exploratory analysis of between groups data.
- C. Recordation and qualitative assessment of adverse events and actions taken by the investigators in response to AEs or SAEs, per IRB requirements.

3. Archival

This study is to be performed in full compliance with the protocol and applicable oversight body and regulatory requirements. All required study documentation and data records will be archived in accordance with preauthorized policies and procedures.

Documentation and data will be stored and archived in a secure format for at least 2 years and for the duration required by the Sponsor and collaborating sites.

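### Does the missing denominator for weekly completion, with early leavers replaceable, bias the primary endpoint?

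*SAP*

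**What the plan says.** The Protocol (section 2) sets the purpose: "This study consists of a feasibility study of the mHealth platform for cognitive training completion in two configurations". It also makes usage data mandatory, listing "required measures of user adherence to the intervention" among what is collected.

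SAP section 2, item A, defines the primary endpoint per Group as the "whole-number percentage of subjects completing minimum usage, per week" and adds: "Mean and standard deviation will be reported for each Group". It gives no denominator, test or success threshold.

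SAP section 1 deals with early leavers: "Any participants who disenroll in the first 2 weeks may be replaced with new subjects (rolling basis) to minimize overall participant loss". It sets no cap on replacements. It continues: "With an enrollment of 30 participants per group, this will allow an additional loss of 5 participants per group", which still meets the final target of 25.

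Item B, the performance endpoint, does name its analysis set: it is calculated "for the subgroup of subjects completing all study weeks per arm".

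**The concern.** Someone who disenrols has, by doing so, failed to complete. Replacing leavers protects the sample for the performance endpoint. When completion itself is being measured, the same rule could remove the failures that the endpoint should count. Item A leaves three readings open:

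1. everyone ever enrolled, including those later replaced;
2. the 30 filled places after replacement;
3. those still enrolled in the week concerned.

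For weeks after a departure, readings 2 and 3 give a higher figure than reading 1. At stake is the main descriptive result of a feasibility study. If early loss differed between Groups I and C, their side-by-side comparison could also be blurred.

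**Working it through.** **The plan's own figures.** 30 − 5 = 25 per group, as stated. 120 / 30 = 4 cells of 30, although only Groups I and C are labelled. If each label pools two cells, all counts double and the percentages and factors below are unchanged.

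**Inputs.** 30 per group and L = 5 later losses come from SAP section 1. The number replaced per group, r, and the number meeting the minimum in a given week, c, are not in the documents. Both are assumptions, shown over a range.

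**Weeks after departure.**
- Reading 1: c/(30 + r)
- Reading 2: c/30
- Reading 3: c/(30 − L) = c/25 once all five later losses have left

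The ratios to reading 1 do not depend on c:
- Reading 2: (30 + r)/30 = 1.03 (r = 1), 1.10 (r = 3), 1.17 (r = 5)
- Reading 3, L = 5: (30 + r)/25 = 1.20 (r = 0), 1.24 (r = 1), 1.40 (r = 5)

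| c | r | Reading 1 | Reading 2 | Reading 3 (L = 5) |
|---|---|---|---|---|
| 15 | 1 | 48.4% | 50.0% | 60.0% |
| 20 | 1 | 64.5% | 66.7% | 80.0% |
| 25 | 1 | 80.6% | 83.3% | 100.0% |
| 15 | 5 | 42.9% | 50.0% | 60.0% |
| 20 | 5 | 57.1% | 66.7% | 80.0% |
| 25 | 5 | 71.4% | 83.3% | 100.0% |

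Reading 2 exceeds reading 1 by 1.6 to 2.7 points at r = 1, and by 7.1 to 11.9 points at r = 5. If nobody leaves, all three readings agree.

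**Weeks 1 and 2.** The direction can reverse, because a leaver may have met the minimum before going. With c = 25, r = 5 and all five leavers meeting it, reading 1 is 30/35 = 85.7% against 25/30 = 83.3% for reading 2.

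**Mean over 8 weeks.** Assume the mean is taken across weekly percentages (the SAP does not say what is averaged), c is the same every week, and leavers met the minimum in weeks 1 and 2. Reading 1 is then [2(c + r) + 6c] / [8(30 + r)] = (8c + 2r) / [8(30 + r)]. Reading 2 exceeds it when 8c(30 + r) > 30(8c + 2r), that is 8cr > 60r, or c > 7.5 (weekly completion above 25%).
- c = 25, r = 5: 210/280 = 75.0% against 83.3%, so reading 2 is higher.
- c = 25, r = 1: 202/248 = 81.5% against 83.3%, so reading 2 is higher.
- c = 5, r = 5: 50/280 = 17.9% against 16.7%, so reading 2 is lower.

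**Which reading the text supports.** Item A refers to subjects without qualification. Item B, next in the same list, restricts to a subset in so many words. A plan that names a subset where it wants one most naturally means all subjects where it names none. That is reading 1, whose inflation is zero. The allowance for five further losses leans towards reading 2, but it explains how enrolment of 30 yields a final 25. It says nothing about who enters item A.

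**The case for a change.** The strongest opposing case is that the percentage is the study's primary result and cannot be interpreted without its denominator. The authors named an analysis set for item B, so silence in A is not simply their habit. The allowance for later loss treats replaced leavers as separate from the five. The 1.20 factor needs no assumption about r. One sentence would settle the matter at almost no cost.

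Part of this stands. The denominator is not written down, the formulas are right, and unequal early loss between groups could matter to a descriptive comparison.

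The rest is weaker. The contrast with item B supports the unrestricted reading of A more than it undermines it. The separate accounting is an inference from sample-size text. The 1.20 factor requires all five later losses to be formal disenrolments. In a remote study, someone who simply stops using the app may stay enrolled, remain in the denominator and count as a non-completer. Completion among those still enrolled is also a legitimate feasibility quantity, though a different one. Counting every departure as non-completion has its own drawback, since some departures have nothing to do with the app. A clarifying sentence would do no harm, but it would record the ordinary reading and leave the analysis unchanged.

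**Conclusion.** No change to the plan follows. This is a gap in wording that an analyst would fill sensibly. The plainest reading of item A counts everyone enrolled in each Group and carries no overstatement, and nothing in either document excludes replaced participants from it. The endpoint is reported descriptively, so no test, threshold or error rate depends on the choice.

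The possible effect is conditional. It is a late-week factor of (30 + r)/30 if replaced leavers were left out, and at most (30 + r)/25, within the SAP's allowance of five, if only those still enrolled were counted. Here r is unknown and the effect is nil when nobody leaves. In weeks 1 and 2 the sign can reverse. For an 8-week mean under the assumptions shown, the 30-place reading overstates only when weekly completion exceeds 25%. The conclusion rests on reading subjects in item A as all enrolled. Text elsewhere that removed replaced participants from item A would reopen the question, but neither document contains any.

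### Task Performance is analysed only in participants who complete every study week, with no all-enrolled analysis beside it; read as a result for everyone enrolled, it is biased if completion is related to performance

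*SAP*

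**What the plan says.** SAP section 2, item B, reports cognition index scores as mean and standard error per Group, "as a differences-based analysis for the subgroup of subjects completing all study weeks per arm". The multi-level model comes later in the same sentence and is not extended to non-completers. The item ends by referring to checks on the model "in an exploratory analysis of between groups data". That last sentence does not repeat the restriction or name the groups compared, but the natural reading is that the restriction carries over.

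The other planned analyses are adverse events (item C) and the primary endpoint (item A), which is summarised "as whole-number percentage of subjects completing minimum usage, per week". Neither measures performance.

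SAP section 1 cites "the need for a final sample of at least 25 participants per group" and says of enrolling 30 that "this will allow an additional loss of 5 participants per group while still achieving the final target sample size". It also provides that "Any participants who disenroll in the first 2 weeks may be replaced with new subjects". The design has "major variables of high/low group intervention/control", and 120 participants at 30 per group implies four groups.

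Protocol section 2 lists "required measures of user adherence to the intervention and requested measures of task performance" and gives no schedule for scoring the index.

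**The concern.** Whether someone completes every week is known only after enrolment, and it is much the same behaviour that the primary endpoint measures. People who do well may be more inclined to stay, or those with little left to gain may leave. In either case the completers' mean differs from the mean for everyone given the application.

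The study is meant to inform later intervention design (Protocol section 1). Its outputs would show how many participants kept up usage, but not whether those who did performed better or worse than the rest. A reader needs that before carrying the performance figure forward.

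Two gaps make the analysis set uncertain as well. Completing all study weeks is not defined: it could mean staying enrolled or meeting minimum usage in each of the eight weeks. And because adherence measures are required while performance measures are only requested, a completer may lack a score and a non-completer may have one. The SAP has no rule for either case.

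**Working it through.** **The plan's own figure.** 30 enrolled less a loss of 5 leaves 25, so retention is 25/30 = 0.833 per group, and 120/30 = 4 groups. This reproduces. The SAP does not say that these 25 are all-week completers. If early leavers are replaced, the share of all ever enrolled is lower still: with 3 replacements in a group (illustrative), 25/33 = 0.758.

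**How many might complete.** Suppose completing means minimum usage in every week, with an assumed 95% meeting it in any one week. If misses are independent, 30 × 0.95^8 = 19.9 complete. If the same people miss each week, 30 × 0.95 = 28.5 complete.

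**Bias of the completer mean against the all-enrolled mean.** Assume a normal propensity to complete that has correlation ρ with the performance measure. For completing share p, the bias in SD units is ρ × φ(z_p)/p, where z_p is the normal quantile of p and φ the normal density. The documents give no value for ρ, so 0.2 to 0.5 is an assumption.

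| Completing | φ(z_p)/p | ρ = 0 | ρ = 0.2 | ρ = 0.5 |
|---|---|---|---|---|
| 28.5/30 = 0.950 | 0.1031/0.950 = 0.109 | 0 | 0.02 | 0.05 |
| 25/30 = 0.833 | 0.2499/0.833 = 0.300 | 0 | 0.06 | 0.15 |
| 19.9/30 = 0.663 | 0.3650/0.663 = 0.550 | 0 | 0.11 | 0.28 |

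A negative ρ reverses the sign. For scale, the standard error of a mean is 1/√25 = 0.20 SD, or 1/√50 = 0.14 SD if Group means configuration (2 × 25).

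**Between-group contrast.** The bias is the difference between the two groups' biases. With equal p and equal ρ it is 0. With 80% against 70% completing it is ρ × (0.497 − 0.350), or 0.03 to 0.07 SD. With 80% against 60% it is ρ × (0.644 − 0.350), or 0.06 to 0.15 SD.

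**What an all-data model would recover.** This was simulated for a per-Group change over time, with 300,000 participants and retention 0.833. Assumed SDs were 0.8 (intercept), 0.6 (gain) and 0.45 (residual), so the change-score SD is √(0.6² + 2 × 0.45²) = 0.875. Dropout followed a logistic model with coefficients 0.5 to 1.5. Bias in SD:

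| Dropout depends on | Completers | All data, weekly scores | All data, start/week 4/end | All data, start/end only |
|---|---|---|---|---|
| Observed gain | 0.05–0.14 | 0.00 | 0.02–0.07 | 0.04–0.12 |
| Underlying gain | 0.06–0.14 | 0.04–0.10 | 0.05–0.12 | 0.06–0.14 |

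With no link between dropout and gain, every bias was within 0.001 of zero. A check at trial size (120 participants, weekly scores, 400 trials per case) agreed. With coefficient 1.0, completer bias of 0.109 fell to 0.014 when dropout followed observed gain, and 0.099 fell to 0.064 when it followed underlying gain (Monte Carlo standard error 0.006). The trial-size data were generated with a linear trend, which favours the model.

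**The case against.** The SAP states its own target. It pre-specifies the completer subgroup, calls the between-groups analysis exploratory, and nowhere offers the result as an all-enrolled estimate. In a feasibility study, performance among people who used the application as intended is a reasonable descriptive question. All of this stands. The bias exists only for a reader who takes the figure as applying to everyone enrolled, and only if completion is related to performance, for which the documents give no evidence.

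It is also fair to say that the SAP does not define its differences as end minus start, and that neither document establishes a baseline cognition index. If the difference is between groups, equal selection in the groups leaves no bias. Even 0.15 SD is below one standard error at 25 per group. That comparison is not fully reassuring, because this bias does not shrink with more participants and the reported standard error does not reflect it.

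The all-data model is not a cure either. With start and end scores only, it removes little or none of the bias. This is a good reason not to replace the declared analysis with it.

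A reader might go further and infer that the completer analysis is invalid, that it necessarily exaggerates performance, or that the comparison of Group I with Group C is biased. The documents support none of these. The summary is correct for completers, the direction of any bias is unknown, and the contrast is affected only if selection differs between the groups.

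**Conclusion.** The point holds as a low-severity gap: the only planned Task Performance analysis conditions on a post-enrolment behaviour, and nothing beside it tells a reader whether the result extends to all enrolled participants.

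Size and sign cannot be determined from the documents. The illustrative range of 0.06 to 0.15 SD applies only if 25 of 30 complete. Widening completion to between 28.5 and 19.9 of 30 gives about 0.02 to 0.28 SD. Both ranges rest on an assumed positive correlation of 0.2 to 0.5, and at zero correlation there is no bias. The lack of a definition of completion and of a rule for missing scores does not add to the bias, but it leaves the analysis set open to more than one reading. The primary endpoint is unaffected.

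**What to change.** In SAP section 2, item B:

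- Keep the completer summary, label it as describing completers, and define what completing all study weeks means.
- State whether the differences are over time or between groups, and give the weeks at which the index is scored. Name the groups in any exploratory contrast.
- Beside the summary, fit the multi-level model already named to every available cognition index score from all enrolled participants, by configuration, with 95% confidence intervals. Include those who leave in weeks 1 and 2, even if they are replaced.
- Tabulate completers against non-completers by group: counts and first available score.
- Add one sensitivity analysis for missing scores, with the shift set in advance on the index scale. For illustration, a shift of −0.5 SD for 5 of 30 participants moves the group mean by 0.5 × 5/30 = 0.083 SD.

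The cost is SAP wording and slightly more analysis. No new data are needed if the application already records scores between start and end. The model relies on scores being missing at random. If scores exist only at start and end it removes little of the bias, and the table and the sensitivity analysis then carry most of the value.
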